## 7.1 Subject Population for Analysis

Analysis populations are defined as following:

**Intent-to-treat population (ITT):** All patients that are randomized to either the ablation treatment or antiarrhythmic treatment are included in the intention to treat population. ITT population is analyzed based on the treatments they are randomized to.

**Per-protocol population:** Patients that satisfy all the inclusion and exclusion criteria, and receive and stay within the randomized treatment during the treatment period are included in the per-protocol. The per-protocol population is analyzed based on the actual treatment they receive.

**Safety population:** All patients that received any ablation treatment **or at least 1 dose of AAD** will be included in the safety population.

# 8 Safety and Adverse Event Reporting

## 8.1 Adverse Event

An **adverse event** (AE) is any new symptom, sign, illness or experience that develops or worsens in severity during the course of the study. Intercurrent illnesses or injuries should be regarded as adverse events. Abnormal results of diagnostic procedures are considered to be adverse events if the abnormality:

- results in study withdrawal
- Is associated with a serious adverse event
- Is associated with clinical signs or symptoms
- Leads to additional treatment or to further diagnostic tests
- Is considered by the investigator to be of clinical significance

### 8.1.1 Unavoidable Adverse Event

Defined as an adverse event inherent to an invasive intervention that is expected to occur for a projected duration in all patients. Unavoidable adverse events are **not** reportable. The adverse events listed are considered unavoidable if the onset occurs within the time frame.

Unavoidable Event Description	Time Frame (after ablation)
Anesthesia related nausea/vomiting	24 hours
Mild to moderate bruising/ecchymosis of catheter puncture site	72 hours
Back pain related to laying on table	72 hours

### **8.1.2 Anticipated Adverse Event**

---

An anticipated adverse event is an adverse event of which the nature, severity or degree of incidence is known and identified in applicable product labeling, published literature, or the Investigational Plan.

### **8.1.3 Unanticipated Adverse Event**

---

An unanticipated adverse event is an advent of which the nature, severity or degree of incidence of which is not known nor identified in applicable product labeling, published literature.

## **8.2 Serious Adverse Event**

---

Adverse events are classified as serious or non-serious. A *serious adverse event* is any AE that is:

- Fatal
- Life-threatening
- Requires or prolongs hospital stay
- Results in persistent or significant disability or incapacity
- A congenital anomaly or birth defect
- Important medical event

Important medical events are those that may not be immediately life threatening, but are clearly of major clinical significance. They may jeopardize the subject, and may require intervention to prevent one of the other serious outcomes noted above. For example, drug overdose or abuse, a seizure that did not result in in-patient hospitalization or intensive treatment of bronchospasm in an emergency department would typically be considered serious.

All adverse events that do not meet any of the criteria for serious should be regarded as *non-serious adverse events*.

## **8.3 Adverse Event Reporting Period**

---

The study period during which adverse events must be reported is normally defined as the period from time of informed consent to the end of the study treatment follow-up.

## **8.4 Preexisting Condition**

---

A preexisting condition is one that is present at the start of the study. A preexisting condition should be recorded as an adverse event if the frequency, intensity, or the character of the condition worsens during the study period.

## **8.5 General Physical Examination Findings**

---

At screening, any clinically significant abnormality should be recorded as a preexisting condition. At the end of the study, any new clinically significant findings/abnormalities that meet the definition of an adverse event must also be recorded and documented as an adverse event.

## **8.6 Post-study Adverse Event**

---

All unresolved adverse events should be followed by the investigator until the events are resolved, the subject is lost to follow-up, or the adverse event is otherwise explained. At the last scheduled visit, the investigator should instruct each subject to report any subsequent event(s) that the subject, or the subject's personal physician, believes might reasonably be related to participation in this study. The investigator should notify the study sponsor of any

CONFIDENTIAL

This document is confidential and the property of The Cleveland Clinic Foundation. No part of it may be transmitted, reproduced, published, or used by other persons without prior written authorization from the study sponsor.

V6.0\_22May2017

death or adverse event occurring at any time after a subject has discontinued or terminated study participation that may reasonably be related to this study.

## **8.7 Abnormal Laboratory Values**

---

A clinical laboratory abnormality should be documented as an adverse event if any one of the following conditions is met:

- The laboratory abnormality is not otherwise refuted by a repeat test to confirm the abnormality
- The abnormality suggests a disease and/or organ toxicity
- The abnormality is of a degree that requires active management; e.g. change of dose, discontinuation of the drug, more frequent follow-up assessments, further diagnostic investigation, etc.

## **8.8 Hospitalization, Prolonged Hospitalization or Surgery**

---

Any adverse event that results in hospitalization or prolonged hospitalization should be documented and reported as a serious adverse event unless specifically instructed otherwise in this protocol. Any condition responsible for surgery should be documented as an adverse event if the condition meets the criteria for an adverse event.

- Hospitalization for worsening of HF should not be reported as an SAE for this trial.

Neither the condition, hospitalization, prolonged hospitalization, nor surgery is reported as an adverse event in the following circumstances:

- Hospitalization or prolonged hospitalization for diagnostic or elective surgical procedures for a preexisting condition. Surgery should **not** be reported as an outcome of an adverse event if the purpose of the surgery was elective or diagnostic and the outcome was uneventful.

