## 3 Study Endpoints

Timeframe to endpoints: After the 3 month treatment period, the endpoints will be assessed for 12 months

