### 3.1 Primary Endpoint

Time to first hospitalization (> 24 hours) for Heart Failure, recurrence of AF or DC cardioversion after the treatment period

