### 3.2 Secondary Endpoints

- Total number of cardiovascular hospitalizations during the trial period for each group
- Time to Recurrence of AF lasting longer than 30 seconds
- Change in distance walked in 6-minute walk test
- Change in the Rand 36-Item Health Survey (SF-36) during trial period
- Change in EF during trial period

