### 6.1 AF Ablation

Experienced electrophysiologists will perform the electrophysiological studies, mapping and ablation for Atrial Fibrillation per guidelines and Standard of care. Ablation targets will be determined by the investigator. Patients already on dofetilide and randomized to ablation may continue taking dofetilide until 2 months post ablation. Other AADs will be stopped 1 week prior to ablation. Dofetilide may be initiated pre-ablation or post ablation but must be stopped 2 months post ablation. Oral anticoagulation will follow AHA/ACC guidelines and will be continued after the PVI procedure for at least 6 months.

Any repeat ablations occurring during the treatment period should be captured on the CRF. If a spiral CT scan was performed, information should be recorded on the CRF. Outcomes will be collected. Primary outcome data in the ablation arm will only be included in the analysis after the treatment period (three months post randomization).

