### 6.2 AAD Treatment

Patients randomized to AAD will receive AADs per Physician and patient preference. Initiation and ongoing clinical evaluations of drug therapy must conform to HRS/ACC/AHA/ ESC guidelines. Oral anticoagulation will follow HRS/ACC/AHA/ESC guidelines. If a patient randomized to the AAD treatment arm has an ablation during the treatment initiation period, the date of ablation will be recorded on the CRF. Outcomes will be collected after the optimization of AAD.

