## **8.9 Recording of Adverse Events**

---

At each contact with the subject, the investigator must seek information on adverse events by specific questioning and, as appropriate, by examination. Information on all adverse events should be recorded immediately in the source document, the appropriate adverse event module of the case report form (CRF) and per sponsor guidelines. Events meeting the definition of serious adverse event (SAE) should be recorded within 24 hours of the sites knowledge of the event. All clearly related signs, symptoms, and abnormal diagnostic procedures results should be recorded in the source document, though should be grouped under one diagnosis.

All adverse events occurring during the study period must be recorded. The clinical course of each event should be followed until resolution, stabilization, or until it has been determined that the study treatment or participation is not the cause. Serious adverse events that are still ongoing at the end of the study period must be followed up to determine the final outcome. Any serious adverse event that occurs after the study period and is considered to be possibly related to the study treatment or study participation should be recorded and reported immediately.

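### Heart-failure admissions before the endpoint window opens are exempt from SAE reporting and outside both hospitalization endpoints, and no between-arm comparison of them is specified

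*Combined protocol and SAP*

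**What the plan says.** **Safety reporting.** By default under Section 8.8, an adverse event that leads to or prolongs a hospital stay "should be documented and reported as a serious adverse event unless specifically instructed otherwise in this protocol". The same section then makes one exception: "Hospitalization for worsening of HF should not be reported as an SAE for this trial". No start or end date is attached to it. Section 8.9 sets the deadline for SAEs: "Events meeting the definition of serious adverse event (SAE) should be recorded within 24 hours of the sites knowledge of the event".

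**Endpoints.** Section 3 fixes the window for all endpoints: "After the 3 month treatment period, the endpoints will be assessed for 12 months". Section 3.1 defines the primary endpoint as "Time to first hospitalization (> 24 hours) for Heart Failure, recurrence of AF or DC cardioversion after the treatment period". The secondary endpoint that counts admissions (Section 3.2) is "Total number of cardiovascular hospitalizations during the trial period for each group", and Section 6 starts the trial period when the treatment period ends.

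**Start of the window by arm.** Section 6.1 states "Primary outcome data in the ablation arm will only be included in the analysis after the treatment period (three months post randomization". For the drug arm, Section 6.2 says only "Outcomes will be collected after the optimization of AAD".

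**The concern.** Taking HF admissions out of SAE reporting is common and defensible when they are counted and compared as efficacy events. That reasoning needs the exemption and the endpoint window to cover the same time, and here they do not. The exemption runs through the whole trial, whereas the window opens only after the treatment period. A three-month blank is customary for AF recurrence, but this plan applies it to HF hospitalization as well.

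The uncovered stretch is the one in which treatment-related HF worsening is most plausible. According to Section 6 it holds repeat ablations and AAD titration, and under most readings the index ablation too. Patients enter with an EF of 20-45% (Section 5.2) and without an HF admission in the previous 3 months (Section 5.3), so an early admission would be a new deterioration. Section 1.1 itself raises the possibility that antiarrhythmic drugs do harm.

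At stake is how a favourable result would be read. A statement that ablation lowers HF hospitalization would rest on a count that begins after the peri-treatment period, with no planned table showing what happened before it.

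**Working it through.** The main check compares rules, not figures.

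**Step 1. Follow one event through the plan.** Take an HF admission of more than 24 hours, six weeks after randomization, in a patient who survives and stays in the trial.
- *SAE by reason of hospitalization?* No. The Section 8.8 exemption applies.
- *Primary endpoint event?* No. Sections 3, 3.1 and 6.1 exclude it.
- *In the cardiovascular hospitalization count?* No. Section 3.2 restricts the count to the trial period.
- *Recorded as an adverse event?* Yes. Sections 8.1 and 8.4 cover worsening of an existing illness, Section 8.3 starts the reporting period at consent, and Section 8.9 requires immediate recording of every adverse event.
- *Recorded as a hospitalization?* Yes, at the 3-6 month visit (Section 6.4.1, item 12).
- *Open to the safety monitor?* Yes. Section 9 includes CRFs and adverse-event forms, reviewed at intervals whose length the protocol does not give.
- *In a specified comparison between arms?* No. Section 7 announces a safety-population analysis but names no safety outcome, time window or test.

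**Step 2. Check where the window starts.** Section 6 runs the treatment period for 3 months from either enrollment or the procedure. Section 6.1 counts from randomization. Section 6.2 ties the drug arm to the end of AAD optimization, with no date. For a patient ablated one month after randomization, the procedure-based reading ends the treatment period at 1 + 3 = 4 months and the randomization-based reading at 3 months. An HF admission between months 3 and 4 is an endpoint event on one reading and uncounted on the other, yet exempt from SAE reporting on both.

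**Step 3. Check the drop-out rule.** Section 7 counts a drop-out for cardiac causes as a primary event at the time of drop-out, with no lower time limit. An early HF admission followed by drop-out could therefore count, while the same admission in a patient who stays would not. That does not fit the window in Sections 3 and 6.1.

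**Step 4. Scale, for illustration only.** The plan states no figure on this point, so only its sample size can be reproduced. For 40% against 60%, two-sided alpha 0.05 and 80% power: {1.96 × √(2 × 0.5 × 0.5) + 0.842 × √(0.4 × 0.6 + 0.6 × 0.4)}² / 0.2² = (1.386 + 0.583)² / 0.04 = 96.9, or 97 per arm against the stated 100. With 220 enrolled at 1:1, there are 220 / 2 = 110 per arm.

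*Assumption A:* 3-10% of patients have an HF admission in months 0-3. Then 0.03 × 110 = 3.3 and 0.10 × 110 = 11, or about 3-11 per arm.

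*Assumption B:* the planned 12-month composite rates (Section 7) arise from a constant hazard that also holds in months 0-3, and HF makes up 10-50% of events. The 3-month risk is q = 1 − (1 − p)^(3/12).

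| Arm | 12-month p | q | q × 110 | HF share 10% | HF share 50% |
|---|---|---|---|---|---|
| Ablation | 0.30 | 0.085 | 9.4 | 0.9 | 4.7 |
| Ablation | 0.40 | 0.120 | 13.2 | 1.3 | 6.6 |
| AAD | 0.60 | 0.205 | 22.5 | 2.3 | 11.3 |

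This gives about 1-7 ablation and 2-11 AAD patients, the same order as A. Neither the 3-10% rate nor the HF share comes from the documents.

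**The case against.** The strongest reply is that nothing is lost. Section 8.8 removes SAE status, not adverse-event status. Early HF worsening goes into the adverse-event module and the hospitalization record, both are held by arm, and the monitor's remit covers both. A fatal or life-threatening HF event meets other SAE criteria in Section 8.2, which an exemption worded for hospitalization does not clearly remove. A safety-population analysis is planned, and a table by arm could be produced at any time. All of this stands.

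Two stronger readings are tempting, and the documents do not support them.

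- *A reader might infer that the monitor would learn of these events only months later, because no 24-hour deadline applies.* The 24 hours in Section 8.9 is a recording deadline that runs from the site's knowledge of the event, and the same section requires immediate recording of every adverse event. The protocol gives SAEs no expedited route to the monitor and does not state the review interval. No delay caused by the exemption can be calculated.
- *A reader might infer that early HF admissions enter no comparison at all.* The safety-population analysis is undefined rather than absent, and the cardiac drop-out rule could bring some of these patients into the primary analysis. What can be said is that no comparison is specified.

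The reply does not show that anyone has committed to comparing early HF admissions between arms, and it offers no reason for the exemption to apply where these admissions are not endpoints. In an unblinded trial, a table that can be chosen later is weaker than one fixed in advance.

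**Conclusion.** The point holds in a limited form. Followed exactly, the plan leaves HF hospitalizations before the endpoint window out of SAE reporting on hospitalization grounds and out of both hospitalization endpoints. They are recorded and open to review, but no between-arm comparison is specified. The length of the uncovered period is itself uncertain, because Sections 6, 6.1 and 6.2 start the window differently and Section 6.2 gives no date.

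The number of patients affected cannot be derived from the documents. On the assumed rates above it is roughly 1-11 per arm. This indicates scale only; it does not predict a difference between arms or its direction. The finding does not invalidate the primary analysis or the sample size. It limits what the trial could claim about HF hospitalization, and it is cheap to put right before the data are analysed.

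**What to change.** 1. **Section 8.8:** limit the exemption to HF hospitalizations that fall inside the endpoint window. Earlier ones then follow the section's own default SAE rule.
2. **Sections 3, 6, 6.1 and 6.2:** reconcile these into one definition of when the window opens, applied to both arms, and refer to it in Section 8.8. A fixed month-3 cut in Section 8.8 alone would not be enough, because under some readings the window opens later and an admission in between would again be both exempt and uncounted. Bring the cardiac drop-out rule in Section 7 into line with the same definition.
3. **Section 7:** tabulate HF hospitalizations by arm from randomization, split at the opening of the window. Add a supportive intention-to-treat analysis of time from randomization to HF hospitalization or death. Death is included because it ends the opportunity for a later admission. The primary endpoint stays as it is.
4. **Section 9:** state the monitor's review interval, so that a reader can tell how soon early events are seen.

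**Cost:** a few additional SAE forms, one table and one model. Hospitalizations are already recorded at both follow-up visits (Sections 6.4.1 and 6.4.2), and deaths are already SAEs under Section 8.2, so no new data collection is needed.

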## **8.9 Recording of Adverse Events**

---

At each contact with the subject, the investigator must seek information on adverse events by specific questioning and, as appropriate, by examination. Information on all adverse events should be recorded immediately in the source document, the appropriate adverse event module of the case report form (CRF) and per sponsor guidelines. Events meeting the definition of serious adverse event (SAE) should be recorded within 24 hours of the sites knowledge of the event. All clearly related signs, symptoms, and abnormal diagnostic procedures results should be recorded in the source document, though should be grouped under one diagnosis.

All adverse events occurring during the study period must be recorded. The clinical course of each event should be followed until resolution, stabilization, or until it has been determined that the study treatment or participation is not the cause. Serious adverse events that are still ongoing at the end of the study period must be followed up to determine the final outcome. Any serious adverse event that occurs after the study period and is considered to be possibly related to the study treatment or study participation should be recorded and reported immediately.

## **8.10 MedWatch Adverse Event Reporting and Product Complaint Reporting**

---

The PI and Institution will be responsible for reporting adverse event information in accordance with FDA regulations for commercially marketed products following standard institutional policy.

If a death or serious injury occurs as a result of a Biosense Webster device malfunction used during the conduct of this study, a MedWatch form should be completed and filed with the FDA per standard institutional reporting policy for commercially marketed medical devices. The PI and institution will simultaneously notify Biosense Webster and C5Research within 24 hours of MedWatch form submission to the FDA. The PI is required to notify Biosense Webster of any and all complaints involving devices used and/or other Biosense Webster products used in the study.

**CONFIDENTIAL**

This document is confidential and the property of The Cleveland Clinic Foundation. No part of it may be transmitted, reproduced, published, or used by other persons without prior written authorization from the study sponsor.

V6.0\_22May2017

For the purpose of this study, serious injury is defined as an unanticipated adverse device effect and definition of complaint is defined in Appendix (A.).

## 9 Safety Monitoring Plan

An independent Safety Medical Monitor will be appointed to monitor the study by reviewing the case report forms, SAE and AE forms at specified intervals throughout the study and will be responsible for the oversight of safety.

## Appendix A: Adverse Event and Complaint Definitions

### Reporting serious adverse events for a marketed device:

Reportable adverse events include death or serious injuries. Serious injuries is defined in FDA regulation as “an injury or illness that: (a) is life-threatening, or (b) results in permanent impairment of a body function or permanent damage to a body structure or (c) Necessitates medical or surgical intervention to preclude permanent impairment of a body function or permanent damage to a body structure” 21CFR803.3.

### Reporting device complaints

A device complaint is defined by the FDA regulation as “any written, electronic, or oral communication that alleges deficiencies related to the identity, quality, durability, reliability, safety, effectiveness, or performance of a device after it is released for distribution” 21CFR820.3(b).

